 - Research assistants will contact the patient by phone to complete assessments. This may be completed at any time from 48 hours to 1 week after surgery.
 - Physical function assessment: we will administer the 6-item Katz index to measure independence in activities of daily living
 - Delirium and cognitive assessment: we will administer a battery of tests to assess (1) cognitive function (overall and particular domains including processing, visual scanning, attention, mental set-shifting, executive function, and verbal memory) and (2) delirium risk
 - Confusion Assessment Method (short form)
 - Montreal Cognitive Assessment (5-minute version)
 - Trail Making Tests Parts A and B
 - Pain assessment: we will administer a 10-point visual analog scale to quantify pain levels related to the hernia
 - Quality of life: we will use the 8-item Carolinas Comfort Scale to

- assess hernia-related quality of life
- Adverse events
- Visit 5 (2-Week Postoperative Visit)
 - Our standard clinical practice is to bring patients back to surgery clinic within 2-4 weeks of surgery to assess recovery and evaluate the incision. This assessment can take place any time in that 2-4 week postoperative period.
 - Vital signs
 - Physical function assessment: we will administer the 6-item Katz index to measure independence in activities of daily living
 - Delirium and cognitive assessment: we will administer a battery of tests to assess (1) cognitive function (overall and particular domains including processing, visual scanning, attention, mental set-shifting, executive function, and verbal memory) and (2) delirium risk
 - Confusion Assessment Method (short form)
 - Montreal Cognitive Assessment (5-minute version)
 - Trail Making Tests Parts A and B
 - Pain assessment: we will administer a 10-point visual analog scale to quantify pain levels related to the hernia
 - Quality of life: we will use the 8-item Carolinas Comfort Scale to assess hernia-related quality of life
 - Adverse events

Indicate treatment and follow-up visit assessments for each visit. List all measurements and procedures in bulleted format.

Include allowable time window in which evaluations may take place, e.g., study visits must be performed on the weeks indicated in the Schedule of Evaluations $\pm X$ days. The evaluation time window should be as narrow as technically feasible.

For example:

- Visit 3:
 - *Vital Signs*
 - *Treatment Administration Form*
 - *Concomitant Medications*
 - *Adverse Events*

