6.2.4 Completion/Final Evaluation

- The final evaluation/completion visit will be done by phone or video at 6 months after surgery, and can be performed any time from 6-9 months after the operation by research assistants
- Evaluations will include
 - Physical function assessment: we will administer the 6-item Katz index to measure independence in activities of daily living
 - Delirium and cognitive assessment: we will administer a battery of tests to assess (1) cognitive function (overall and particular domains including processing, visual scanning, attention, mental set-shifting, executive function, and verbal memory) and (2) delirium risk
 - Confusion Assessment Method (short form)
 - Montreal Cognitive Assessment (5-minute version)
 - Trail Making Tests Parts A and B
 - Pain assessment: we will administer a 10-point visual analog scale to quantify pain levels related to the hernia
 - Quality of life: we will use the 8-item Carolinas Comfort Scale to assess hernia-related quality of life
 - Adverse events or serious adverse events

List each assessment to be performed at the participant's final visit.

Specify evaluations needed for participants who discontinue study intervention early. Specify potential reasons for early termination. Specify any requirements (e.g., related to monitoring and reporting of adverse experiences) for follow-up on participants once they have stopped using the study intervention.

7 **SAFETY ASSESSMENTS**

Participant safety should be monitored once an individual is enrolled in the study. To assure comprehensive review of potential safety events, include an alphabetical list of expected adverse experiences for each study intervention, criteria for management and modification of the study intervention regimen or participant assessments if an adverse event occurs.

For investigational drug studies the section should identify toxicities that have been seen in previous studies.

7.1 **Specification of Safety Parameters**

Safety is a significant concern for our team. Overall, the risk for both arms is low, but there is potential risk both from surgery and anesthesia. At each study visit, we will actively examine for and inquire about possible adverse and serious adverse events. Specifically, we will monitor for the following to record in the adverse events database for review:

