7.2 Methods and Timing for Assessing, Recording, and Analyzing Safety Parameters

7.2.1 Assessing and recording

At each study visit, research assistants will actively elicit evidence of SAE and AE by asking questions related to symptoms and conducting physical exam in conjunction with the clinical team (which should be examining for these complications as well up to the 2 week postoperative time point). For the 6 month visit, symptoms will be elicited by asking questions via phone. At each time point, after reviewing the list of SAE and UE, an open-ended question will be asked regarding whether the patient is having any other additional problems or concerns. Any SAE/AE will be conveyed to the clinical team if not already identified, documented in the research record, and referred to the data safety and monitoring board immediately upon ascertainment.

Information to be collected includes event description, time of onset, severity, relationship to study arm, and time of resolution/stabilization. All AE occurring during the study will be documented regardless of relationship to study assignment and all will be followed to adequate resolution

Any medical condition present at the time of screening will be considered as patient baseline and will not be reported as an AE. If the condition deteriorates during the study, it will be recorded as an AE. UP will be recorded in the research record throughout the study. Changes in severity of an AE will be recorded to allow an assessment of duration at each level of severity to be performed. AE found to be intermittent will have documentation of each episode onset and duration. We will record all events with start dates occurring after informed consent until 30 days after the last date of study participation.

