9.1.4 Primary outcomes and hypotheses

- 1) Outcome: Rates of enrollment
 - a. Hypothesis: Based on our preliminary data, at least 75% of eligible patients will agree to be randomized.
- 2) Outcome: Proportion of participants completing all study visits
 - a. Hypothesis: We will be able to follow 100% of patients up to their 2 week postoperative visit (as essentially all patients keep this appointment in our clinical practice), and we will be able to follow at least 90% of patients at the six month time point.
- 3) Outcome: Proportion of missing data
 - a. Hypothesis: Missing data on study instruments will be <5%
- 4) Outcome: Time to complete study evaluations and instruments
 - a. Hypothesis: Total time to complete each study evaluation will be acceptable to patients and <30 minutes.
- 5) Outcome: Participant satisfaction with study procedures and instruments
 - a. Hypothesis: Overall time burden for instrument completion will be acceptable to patients

- 6) Outcome: Whether survey instruments can be eliminated due to redundancy
 - b. Hypothesis: One or more study instruments can be eliminated (thus reducing the time burden) because the other instruments may predict a substantial portion of variance
- (7) Outcome: Estimate sample size for fully powered randomized trial.
 - a. Hypothesis 1: Using data from the pilot study, we will be able to establish stable estimates of the necessary sample size for a randomized trial.
 - b. Hypothesis 2: We will be able to identify the optimal primary outcome for a multisite randomized trial by balancing the necessary sample size needed to adequately power the study versus the clinical significance of each outcome.

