9.1.5 Secondary outcomes and hypotheses

Again note that this pilot trial is not powered to detect differences in the secondary (clinical) outcomes described below. Our hypotheses reflect expected findings for a larger, multisite randomized clinical trial that will follow this pilot study.

- 1) Outcome: Quality of life
 - a. Hypothesis: quality of life will be significantly improved when older adults have their inguinal hernias repaired under local rather than general anesthesia.
- 2) Outcome: Physical function
- 3) Hypothesis: physical function (activities of daily living) will be significantly improved when older adults have their inguinal hernias repaired under local rather than general anesthesia.
- 4) Outcome: Cognitive function
 - a. Hypothesis: Cognitive function will be significantly improved when older adults have their inguinal hernias repaired under local rather than general anesthesia.
- 5) Outcome: Pain
 - a. Hypothesis: Pain will be similar for older adults having hernia surgery regardless of anesthesia modality.
- 6) Outcome: Postoperative complications
 - a. Hypothesis: The overall incidence of postoperative complications will be significantly reduced when older adults have their inguinal hernias repaired under local rather than general anesthesia. This will mostly be due to decreased rates of urinary retention (a common complication of general anesthesia).
- 7) Outcome: Operative and anesthesia times
 - a. Hypothesis: Time for surgery (incision to closure) and anesthesia (enter to exit operating room) will be significantly decreased when older adults have their inguinal hernias repaired under local rather than general anesthesia.
- 8) Outcome: Recovery time (time spent in the post-anesthesia care and stepdown units)
 - a. Hypothesis: Time spent in the post-anesthesia care and stepdown units after surgery will be significantly decreased when older adults have their inguinal hernias repaired under local rather than general anesthesia.

State the statistical hypotheses.

Describe the reasons for choice of study design (e.g., parallel groups, crossover, immediate versus deferred intervention, factorial, large simple trial, equivalency or non-inferiority trial); why certain design features were chosen (e.g., for a crossover trial, how the length of the washout period was chosen).

Describe the primary and secondary hypotheses and the primary and secondary outcome measures as well as their validity and reliability.

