9.4.2 Secondary outcomes

Timing of measurements for secondary outcomes is outlined in the schedule of evaluations (section 6.1). Instruments are briefly summarized in [Table 3](#) below.

- 1) Outcome: Quality of life
 - a. Measurement: The Carolinas Comfort Scale (CCS) was developed specifically to measure quality of life in patients having hernia repair.²³ The instrument consists of 8 items on a 6-point Likert-type scale. The Cronbach's alpha was 0.979 in the original development paper and 0.95 on a subsequent international validation study.²¹ The CCS demonstrates superior discrimination when compared to generic quality of life instruments (SF-36), with reasonable test-retest reliability (kappa coefficients for questions range from 0.40-0.60 for all but 1 item. Additionally, the CCS is used as the primary quality of life instrument for the International Hernia Mesh Registry because it can be rapidly administered, is well accepted by patients, is highly reliable, and typically has only 10-15% missing data when used for the international registry.²¹ The CCS can be scored as a summary of all items and as a binary score for the presence or absence of symptoms. We will use a 0.5 standard deviation difference on the continuous scale as the minimal clinically important difference.²⁴
 - b. Timing: The CCS will be measured at baseline, 48 hours after surgery, at 2 weeks after surgery, and at 6 months after surgery.
- 2) Outcome: Physical function
 - a. Measurement: We will measure independence in activities of daily living with the 6-item Katz Index, a long-established measure for physical/functional status for individuals expected to have at least some degree of disability.²⁵ Prior work demonstrates coefficients of scalability ranging from 0.74-0.88, indicating the Katz Index offers a useful cumulative scale.²⁵ We will score the instrument on a 0-6 scale, indicating the number of activities where the participant is partially or fully dependent. A 0.5 standard deviation difference will again represent the minimal clinically important difference.²⁴
 - b. Timing: Measurement will occur at baseline, at 2 weeks after surgery, and at 6 months after surgery.
- 3) Outcome: Cognitive function and delirium
 - a. Measurement

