- iv. Neuralgia/chronic pain: if patients experience pain at/near the site of surgery for >3 months after the operation, they are considered to have neuralgia. This will be managed initially by consultation with the pain service for injection of steroids and local anesthetic at the site for up to 3 times. If this proves unsuccessful, the patient will be considered for surgical neurectomy.
- v. Spermatic cord injury or orchitis: during surgical repair, the spermatic cord (including vas deferens, spermatic artery, venous plexus) are mobilized away from the hernia sac. If the surgeon identifies injury (division of the vas deferens, bleeding from artery or veins that requires intervention beyond holding pressure) or if there is involution of the testicle on the side of the surgery (identified by pain beyond the ordinary, swelling in the groin, ultrasound showing no flow) then we will categorize as a spermatic cord injury. Intraoperatively, a vas deferens injury will result in consultation of urology for repair. Arterial and venous injuries are generally too small to repair intraoperatively, but vascular surgery service can be consulted for evaluation. Postoperatively, there is no treatment for cord injury other than pain control, urologic evaluation, and possible removal of testicle on the injured side.
- vi. Urinary retention: per our standard hospital protocol, if patients are unable to urinate by four hours after surgery, we will perform a bladder scan. If >200 mL of urine is seen, the patient will receive an in-and-out catheterization followed by observation for up to an additional four hours. If the patient is still unable to urinate, they will have a Foley catheter placed, be admitted for overnight observation, and be evaluated by urology. Typically, the patient goes home with a Foley leg bag and undergoes urodynamic testing 1 to 2 weeks later after being discharged with medication for benign prostatic hypertrophy. The occurrence of urinary retention will not change the study intervention regimen or the schedule of participant assessments.

- vii. Reoperation: Any unplanned surgery after the participant leaves the operating room following repair of the hernia.
- viii. Unplanned readmission or emergency room visit: Any admission for a planned outpatient surgery, or any hospital admission or emergency room visit that occurs after discharge.

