xxvii. Deep wound surgical site infection: infection that occurs within 30 days after the operation and the infection appears to be related to the operation and infection involved deep soft tissues (e.g., fascial and muscle layers) of the incision and at least one of the following:

- Purulent drainage from the deep incision but not from the organ/space component of the surgical site.
- A deep incision spontaneously dehisces or is deliberately opened by a surgeon when the patient has at least one of the following signs or symptoms: fever (> 38 C), localized pain, or tenderness, unless site is culture-negative.
- An abscess or other evidence of infection involving the deep incision is found on direct examination, during reoperation, or by histopathologic or radiologic examination.
- Diagnosis of a deep incision SSI by a surgeon or attending physician.

-Note:

- Infection that involves both superficial and deep incision sites will be categorized as deep incisional SSI.
- An organ/space SSI that drains through the incision will be categorized as a deep incisional SSI.

b. Timing: Postoperative complications will be assessed prior to discharge and at the 2 week postoperative visit. Complications will be coded as present if identified at any time between the surgery and the 2 week visit.

6) Outcome: Operative and anesthesia times

- a. Measurement: Operative time will be recorded as the difference, in minutes, between the time of skin/wound closure and the time of surgical incision. Anesthesia time will be recorded as the difference, in minutes, between the time patients exit the operating room and the time of entrance to the operating room.
- b. Timing: Anesthesia intraoperative records routinely capture all four time points necessary to calculate the above outcomes. Records are scanned into the electronic medical record on the day of surgery and this data will be entered into the research record by research assistants on the day of surgery

(once the operation is complete).

- 7) Outcome: Recovery time (time spent in the post-anesthesia care and stepdown units)

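### The complications outcome lists neuralgia, defined by more than 3 months of pain, but its coding window closes at the 2-week visit, so the item cannot be coded as present in either arm

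*Combined protocol and SAP*

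**What the plan says.** - **Coding rule** (9.4.2, outcome 5, Timing). There are two assessment points, before discharge and the 2-week visit. Then: "Complications will be coded as present if identified at any time between the surgery and the 2 week visit".
- **Neuralgia** (9.4.2, outcome 5, item iv): "if patients experience pain at/near the site of surgery for >3 months after the operation, they are considered to have neuralgia". Section 7.1.4 repeats this definition in its list of adverse events that can occur under either type of anesthesia.
- **Date of the 2-week visit** (6.2.3, Visit 5): the clinic return is planned 2 to 4 weeks after surgery, and "This assessment can take place any time in that 2-4 week postoperative period".
- **Later contact.** The section 6.1 schedule ticks adverse events at every visit from surgery to the 6-month final visit. The final evaluation in 6.2.4 includes "Adverse events or serious adverse events" and may be held 6 to 9 months after surgery. Section 7.2.1 adds: "For the 6 month visit, symptoms will be elicited by asking questions via phone".
- **Intended use.** The complications hypothesis in 9.1.5 is that "The overall incidence of postoperative complications will be significantly reduced" under local anesthesia, mostly through less urinary retention. Section 9.1.4 (outcome 7, hypothesis 2) says: "We will be able to identify the optimal primary outcome for a multisite randomized trial". Section 9.4.1 (outcome 7) plans to estimate proportions with 95% confidence intervals for categorical variables, as input to the sample size of the larger trial.

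**The concern.** One component of the outcome needs more than 3 months of follow-up, and the rule for coding the outcome allows at most 4 weeks. A patient who develops neuralgia cannot be recorded as having it in the outcome that names it.

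The pilot exists to test outcome measurement before a multisite trial and to supply proportions for its design. A zero produced by the coding rule would look the same, in a table of complications by arm, as a zero produced by a rare event. Someone using that table to plan the larger trial could conclude that neuralgia is uncommon after both types of anesthesia, when the pilot outcome had no means of showing otherwise.

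**Working it through.** The plan gives no figure to reproduce. The check compares time windows.

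**Inputs**

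| Quantity | Value | Source |
|---|---|---|
| Coding window opens | surgery, day 0 | 9.4.2, outcome 5, Timing |
| Coding window closes | 2-week visit, day 14 to day 28 | 9.4.2 with 6.2.3, Visit 5 |
| Neuralgia definition | more than 3 months after surgery | 9.4.2, item iv; 7.1.4 |
| Final contact | 6 to 9 months after surgery | 6.2.4 |
| Patients | 40 per arm, 80 in all | 9.2.1 |
| Hypothesised 6-month retention | at least 90% | 9.1.4, outcome 2 |

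**Step 1. Earliest day on which the definition can be met.** 3 × 365.25 / 12 = 91.3 days.

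**Step 2. Gap to the close of the window.** With the visit on day 14: 91.3 − 14 = 77.3 days. With the visit on day 28: 91.3 − 28 = 63.3 days. The gap is positive across the whole permitted range, so a late clinic date does not help.

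**Step 3. Consequence for the count.** The number of patients coded with neuralgia is 0 of 40 in each arm, whatever patients experience. The comparison of proportions in 9.5.2 has nothing to compare for this item. A confidence interval around that zero would describe sampling error in a count that the rule has already fixed, so none is given here.

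**Step 4. Can the trial observe the item elsewhere?** The final contact falls between 6 × 365.25 / 12 = 182.6 days and 9 × 365.25 / 12 = 273.9 days, after day 91.3. It is the only scheduled contact after that day. Adverse events are elicited there, neuralgia is on the adverse event list with the same definition, and 7.2.1 has onset and resolution times recorded, which is what the definition needs. The information is collected, but nothing in 9.4.2 or 9.5 carries it into outcome 5.

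**Step 5. Denominator if the item is coded at the final contact.** 0.90 × 80 = 72 patients, or 36 per arm if losses are equal.

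**The case against.** Several points on the other side are sound.

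- **The rule does not contain the word only.** It says when a complication is coded as present and does not spell out what happens to one found later. That is true, but the sentence before it names just two assessment points, and no other text provides for later coding. The natural reading is a closed window.
- **Neuralgia is recorded as an adverse event, and pain and hernia-related quality of life are measured at 6 months.** This stands and limits the harm. It does not repair the complications outcome, because no rule moves a late adverse event into it.
- **A complications outcome may have a shorter window than adverse event reporting.** This also stands. A reader might infer that the 2-week rule contradicts the section 6.1 schedule, to which the opening of 9.4.2 refers for timing. The documents do not support that: the outcome-specific rule is the more specific of the two. The problem is one listed item that cannot occur inside the window.
- **The comparison is exploratory** (9.1.3), and urinary retention, the expected driver of any difference, is identified within the window. Both are correct.

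A reader might also infer that overall complication incidence is understated by some number of percentage points. The documents give no rate for neuralgia, and 9.4.2 does not define an any-complication composite, so any such figure would rest on assumed rates. Nor do they support a claim of bias between arms, since the same rule applies to both.

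Finally, the 30-day limits in the definitions of sepsis and surgical site infection might be read as a second conflict. They are upper bounds, which can coexist with an earlier cut-off.

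**Conclusion.** The defect is real and minor. Under the stated rule, neuralgia is a structural zero in both arms. The window closes 63 to 77 days before the definition can be met, and the complications outcome gives no usable estimate for this item. The conclusion rests on reading the coding rule as a closed window and on the 2-to-4-week limit for the clinic visit. It needs no assumption about event rates.

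It goes no further than that. The effect on overall complication incidence is not quantified, no distortion of the comparison between arms is claimed, and the other listed complications are outside this point. What makes it worth correcting is that a pilot meant to test outcome measurement already holds the information and leaves it out of the outcome that names it.

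**What to change.** Amend the Timing paragraph of outcome 5 in 9.4.2 along these lines:

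*Neuralgia (item iv) is exempt from the 2-week cut-off. It is coded from the adverse event interview at the 6-month contact, using the definition in item iv, and reported as a separate 6-month proportion by arm. The 2-week complication incidence is reported alongside it and labelled as excluding neuralgia. Patients without the 6-month contact are coded as missing for this item, not as absent.*

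Coding them as missing agrees with the complete-case approach in 9.5.3.

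The cost is small. The contact and the interview already exist, so no visit or instrument is added and no clinical rule changes. There are two drawbacks. The denominator falls to about 72 of 80 if 6-month retention is 90%, and the item then rests on patient report by phone or video, without an examination. Both should be stated where the proportion is reported.
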